8.3.2. Method of Detecting TEAEs and TESAEs

The method of recording, evaluating, and assessing causality of TEAEs and TESAEs, and the procedures for completing and transmitting SAE reports are provided in Section [10.2](#), Appendix 2.

Care will be taken not to introduce bias when detecting TEAEs and/or TESAEs. Open-ended and non-leading verbal questioning of the Participant is the preferred method to inquire about TEAE occurrences.

8.3.3. SAE Reporting to the Sponsor or Designee

All SAEs should be reported to the Sponsor or designee within 24 hours of knowledge of the SAE occurring (see Section 10.2, Appendix 2).

8.3.4. Adverse Events of Special Interest

Any of the AESIs that occur during the study, as described below, must be recorded as AESI and any of the AESI that meet the criteria for a serious event (Section 8.3) must be reported as a TESAE and identified as an AESI.

Categories of AESIs

There are two main categories of AESIs as presented below: 1) those considered to be related to the angiogenesis potential of Engensis, 2) other medical problems in this patient population, and 3) COVID-19 infections occurring in Participants during the study.

8.3.4.1. AESI Considered Related to AngiogenesisAtherosclerosis

Hyperplasia of the vasa vasorum in the early stages of atherosclerosis is independent of angiogenesis, but the intimal neovascularization that follows the hyperplasia of the vasa vasorum is angiogenesis-dependent.⁶⁶ Angiogenesis increases oxygen and nutrients to the artery wall and supports initial plaque growth. Once the atherosclerotic plaque develops, intimal angiogenesis is thought to contribute to characteristics of an unstable plaque, plaque hemorrhage, and plaque rupture. Therefore, diagnoses suggestive of recent coronary artery disease since Baseline will be evaluated as AESIs.

Cancer

Angiogenesis plays an important role in the proliferation and metastatic spread of cancer as these processes are dependent on an adequate supply of oxygen and nutrients and removal of waste products.⁶⁷ All types of cancer reported during the study will be deemed to be AESIs.

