2.3. Benefit/Risk Assessment

2.3.1. Risk Assessment

The risks for the study medication and study procedures are summarized in the following table.

Potential Risk of Clinical Significance	Summary of Data/Rationale for Risk	Mitigation Strategy
Risks of Engensis		
Cancer Patients with melanoma and tongue cancer appear to be at an increased risk of death due to ALS⁶²	Angiogenesis plays an important role in the proliferation and metastatic spread of cancer as these processes are dependent on an adequate supply of oxygen and nutrients and removal of waste products.	Participants who develop any type of cancer during VMALS-002-2 will be followed long-term in VMALS-002-2b
Angiogenesis	Intimal angiogenesis in atherosclerotic plaques contributes to unstable plaque, plaque hemorrhage, and plaque rupture that predisposes to thrombotic or embolic events.	Participants who have experienced a stroke, cerebrovascular accident, or myocardial infarction within 3 months before Screening for VMALS-002-2 and Participants with peripheral artery disease (PAD) or PAD requiring revascularization will be excluded from VMALS-002-2b
Risks of Study Procedures		
Complications of venipuncture (for blood draws for laboratory tests)	Venipuncture complications include minor bruising, hypotension, and syncope.	Incidence of adverse events of bruising, hypotension, and syncope will be closely monitored throughout the study.

Adverse Events in Clinical Studies

Engensis has been well tolerated in all clinical studies conducted thus far in more than 500 Participants. The preponderant adverse events have consisted of mild, transient injection site effects, including itching, erythema, pain, and muscle spasms. Other TEAEs that have been reported were generally mild to moderate. Refer to the IB for a table of AEs that occurred in $\geq 2\%$ of trial Participants.

Five SAEs have been reported to date as possibly related to study treatment:

- Colon cancer in the Phase 1 trial of CLI (assessed by the investigator to be possibly related to study drug and, even though the sponsor noted that the Participant had a history of colon polyps, a relationship to study drug could not be ruled out)
- Peroneal deep vein thrombosis (categorized as possibly related to the study injection) in the Phase 2 trial of CLI. The mechanism by which HGF or VM202 could be causative is not established.

SAEs reported as possibly related in the VMDN-003 trial included:

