- Vitreous hemorrhage of the eye (categorized as possibly related to the study drug but was probably related to underlying disease)
- Myocardial infarction (categorized by Helixmith as possibly related to the study drug, although categorized by the investigator as not related to the study drug)
- Adenocarcinoma (categorized as possibly related to the study drug by the investigator and not related to the study drug by Helixmith)

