6.14.1.3 Adverse Events of Special Interests (AESI)

There are 3 main categories of AESIs as presented below:

- a) considered to be related to the angiogenesis potential of Engensis
- b) other medical problems in this patient population
- c) COVID-19 infections occurring in Participants during the study

AESI Considered Related to Angiogenesis

Atherosclerosis

Hyperplasia of the vasa vasorum in the early stages of atherosclerosis is independent of angiogenesis, but the intimal neovascularization that follows the hyperplasia of the vasa vasorum is angiogenesis-dependent. Angiogenesis increases oxygen and nutrients to the artery wall and supports initial plaque growth. Once the atherosclerotic plaque develops, intimal angiogenesis is thought to contribute to characteristics of an unstable plaque, plaque hemorrhage, and plaque rupture. Therefore, diagnoses suggestive of recent coronary artery disease since Baseline will be evaluated as AESIs.

QMD Ref: Worldwide-TMP-ST-005-7.0 Effective: 12Aug2019	Governing QMD: Worldwide-SOP-ST-001
Confidentiality Statement	

This document is the property of Worldwide Clinical Trials Inc. and may not be duplicated, copied, altered or removed from company without prior approval from Worldwide Quality Assurance or in compliance with Worldwide Standard Operating Procedures.

Worldwide Clinical Trials Controlled Quality Management Document			
 WORLDWIDE CLINICAL TRIALS	Sponsor:	Helixmith Co., Ltd.	
	Protocol Number:	VMALS-002-2b	
STATISTICAL ANALYSIS PLAN. PHASE 2-3-4			

Cancer

Angiogenesis plays an important role in the proliferation and metastatic spread of cancer as these processes are dependent on an adequate supply of oxygen and nutrients and removal of waste products. All types of cancer reported during the study will be deemed to be AESIs.

Other Medical Problems in ALS Patients

- Pulmonary Medical Problems: Because patients with ALS are at an increased risk to develop pulmonary medial problems such as aspiration of food or liquids, pneumonia, and respiratory arrest, all events of this type that occur during the study will be considered AESIs.
- Progressive Muscle Weakness: Because some patients with ALS may develop rapidly progressive muscle weakness that results in loss of ability to care for self, decubitus ulcers, or weight loss due to impaired deglutition, all events of this type that occur during the study will be considered AESIs.

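### The angiogenesis AESI category covers only coronary disease and cancer, so strokes and peripheral arterial events, which fall within the protocol's own risk rationale, would be missing from the AESI count

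*Protocol*

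**What the plan says.** Protocol 8.3.4.1 explains how new vessels in the arterial intima can destabilise plaque, and concludes that "diagnoses suggestive of recent coronary artery disease since Baseline will be evaluated as AESIs". The other half of the category is cancer: "All types of cancer reported during the study will be deemed to be AESIs". SAP 6.14.1.3 repeats both rules and adds no list of terms.

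The angiogenesis row of the risk table in Protocol 2.3.1 states the hazard without limiting it to the heart: "Intimal angiogenesis in atherosclerotic plaques contributes to unstable plaque, plaque hemorrhage, and plaque rupture that predisposes to thrombotic or embolic events". Its mitigation column excludes "Participants who have experienced a stroke, cerebrovascular accident, or myocardial infarction within 3 months before Screening for VMALS-002-2", and also participants with peripheral artery disease (PAD).

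The same section lists five SAEs reported as possibly related: colon cancer, deep vein thrombosis, vitreous hemorrhage, myocardial infarction and adenocarcinoma.

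AESI incidence, Engensis against Placebo, is one component of the primary endpoint, together with TEAE and TESAE incidence (Protocol 3 and 9.3.1; SAP 3.1). SAP 6.14.1.4 plans one AESI table, 14.3.1.9, by system organ class and preferred term.

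**The concern.** The argument in 8.3.4.1 concerns the artery wall in general, but its conclusion covers only the coronary arteries. Neither document says why cerebral and peripheral arteries are left out, although 2.3.1 names conditions of both.

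The stake is the AESI component. Followed as written, the rule would not flag a stroke or a peripheral arterial occlusion, and Table 14.3.1.9 would omit it. In the general TEAE table such events would sit in separate rows by preferred term, with nothing linking them to the stated mechanism.

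The AESI table also merges three kinds of event: those tied to angiogenesis, those expected in ALS (pulmonary, muscle weakness, bulbar) and COVID-19. Its total therefore does not answer the question the angiogenesis category was created for.

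Because safety is not formally tested, a grouping fixed in advance is the main safeguard against choosing groupings after the treatment codes are known.

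**Working it through.** The plan gives no power, alpha or event-rate figure on this point, so there is nothing to reproduce. The check sets the passages side by side.

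**Step 1: risk text against AESI rule**

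| Event type | Protocol 2.3.1 | AESI under 8.3.4.1? |
|---|---|---|
| Cancer | Own risk row; 2 listed SAEs | Yes |
| Coronary (e.g. myocardial infarction) | Exclusion condition; 1 listed SAE | Yes |
| Stroke, cerebrovascular accident | Exclusion condition; no listed SAE | No |
| PAD, peripheral arterial event | Exclusion condition; no listed SAE | No |
| Other non-coronary arterial thrombosis or embolism | Within the stated hazard; no listed SAE | No |
| Venous thrombosis | 1 listed SAE; not described as a result of plaque rupture | No |
| Ocular hemorrhage | 1 listed SAE; not described as a result of plaque rupture | No |

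The ALS and COVID-19 categories (8.3.4.2, 8.3.4.3) name none of the types marked No. The pulmonary list in 8.3.4.2 is open-ended, so a pulmonary embolism might be flagged there by judgement.

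**Step 2: the five listed SAEs**

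Inside the definition: colon cancer, adenocarcinoma, myocardial infarction = 3 of 5. Outside: "Peroneal deep vein thrombosis (categorized as possibly related to the study injection) in the Phase 2 trial of CLI" and "Vitreous hemorrhage of the eye" = 2 of 5 (40%).

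Both cases outside are caveated. The protocol says that the mechanism by which the product could cause the thrombosis is not established, and that the hemorrhage was probably related to underlying disease. None of the five is a non-coronary arterial event. The arterial gap therefore rests on the stated mechanism and the named conditions, not on prior cases.

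Adding only non-coronary arterial events would leave coverage at 3 of 5. Adding the venous and ocular terms as well would bring it to 5 of 5.

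**Step 3: where an unflagged event would appear**

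It would be in Table 14.3.1.2 and Listing 16.2.7.1; if serious, also in Table 14.3.1.3 and Listing 16.2.7.3; if judged related, also in Listing 16.2.7.5. It would not be in Table 14.3.1.9 or the AESI listing, 16.2.7.2.

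**Step 4: how often this could matter**

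The documents give no event rate, so the per-participant rates p below are assumptions. With n = 18 (the maximum, both arms together):

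P(at least one) = 1 − (1 − p)^18

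P(at least two) = 1 − (1 − p)^18 − 18p(1 − p)^17

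| Assumed p | At least one | At least two |
|---|---|---|
| 1% | 16.5% | 1.4% |
| 2% | 30.5% | about 5% |
| 5% | 60.3% | about 23% |

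Zero events in 18 leaves a one-sided 95% upper limit of 1 − 0.05^(1/18) = 15.3%.

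A single unflagged event already changes the AESI figure. Grouping helps to reveal a pattern only when at least two participants are affected.

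**The case against.** The strongest reply is that nothing is lost. With at most 18 participants, every TEAE and TESAE is listed individually. The DSMB sees all reported events, may read narratives and can request unblinded data. Expected ALS progression is not a TEAE unless more severe than expected (Protocol 10.2.1), and a table by system organ class and preferred term keeps different kinds of event on different rows. On plausible rates, two or more such events are unlikely.

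Much of this stands, and it rules out four stronger readings that a reader might infer:

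- **That these events drop out of the primary endpoint.** They do not; the TEAE and TESAE components capture them. Only the AESI flag and its table are affected.
- **That thrombotic events as a class are uncovered.** Coronary events such as myocardial infarction are covered.
- **That 40% measures the damage.** It is two case reports, both caveated, from a programme of more than 500 participants. It is not an effect on this trial's results.
- **That a signal can be seen only if events are grouped, or that ALS events swamp the AESI total.** Individual listings contradict the first. The second is plausible but has no figure behind it. The SAP's list of tables is not readable in the public version, so further subdivision of the AESI output cannot be excluded.

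The reply does not explain why an arterial mechanism stated in general terms yields a coronary-only rule. Nor does it remove the fact that AESI incidence is a named primary component whose content depends on that rule.

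**Conclusion.** The point holds as a gap between the protocol's risk rationale and its AESI definition. Non-coronary arterial events fall within the hazard described in 2.3.1 but outside 8.3.4.1 and SAP 6.14.1.3. They would be missing from the AESI component of the primary endpoint and from Table 14.3.1.9, which, as described, also does not split AESIs into the three categories.

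The size is small. TEAE and TESAE incidence, sample size and error rates are unaffected. What changes is the AESI count, and only if such an event occurs: a 16.5% to 60.3% chance of at least one at assumed rates of 1% to 5%, with all 18 participants enrolled.

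The conclusion assumes that the coronary wording is applied literally. The case for venous thrombosis and ocular hemorrhage is weaker, resting on one caveated case each. The change is worth making because it is cheap and must be fixed before unblinding to be credible.

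**What to change.** 1. Reconcile Protocol 2.3.1 with Protocol 8.3.4.1 and SAP 6.14.1.3: either carry the non-coronary arterial hazard into the AESI text or state why those events are not of special interest.
2. In the SAP, before unblinding, add a supplementary angiogenesis grouping as an extra block in Table 14.3.1.9. Define it by a fixed MedDRA term list covering non-coronary arterial thrombotic or embolic, cerebrovascular and peripheral arterial events.
3. Report AESI incidence by arm for each of the three categories as well as in total.
4. Optionally, add venous thrombosis and ocular hemorrhage as a sensitivity grouping, with a footnote giving the single prior case behind each and its caveat.

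The cost is one term list and extra rows in a planned table; the events are already collected as TEAEs. If the wider grouping were counted as AESIs, the total could rise slightly and might no longer match the core study, whose AESI list is not in these documents. That matters because SAP 6.14.1 plans a tabulation pooling TEAEs from both studies. Keeping the existing AESI definition as the main count, with the new grouping beside it, avoids both problems.

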8.3.4.2. Other Medical Problems in ALS Patients

Several medical problems are frequently observed in patients with ALS that should be considered AESIs. These medical problems are listed below.

- Pulmonary Medical Problems: Because patients with ALS are at an increased risk to develop pulmonary medial problems such as aspiration of food or liquids, pneumonia, and respiratory arrest, all events of this type that occur during the study will be considered AESIs.

- **Progressive Muscle Weakness:** Because some patients with ALS may develop rapidly progressive muscle weakness that results in loss of ability to care for self, decubitus ulcers, or weight loss due to impaired deglutition; all events of this type that occur during the study will be considered AESIs.
- **Bulbar Disease:** Participants may develop bulbar disease or worsening on bulbar disease during the study, manifested as challenges with dysarthria, facial weakness, impaired tongue pulsion or palate elevation, and impaired mastication and swallowing; all of these types of events that occur during the study will be considered AESIs.

8.3.4.3. COVID-19 Infections

A diagnosis of a Corona Virus Disease 2019 (COVID-19) infection occurring in Participants will be recorded as an AESI and their disposition during the trial following the diagnosis of the COVID-19 infection will be tracked.

8.3.5. Follow-up of TEAEs, TESAEs, and AESIs

After the initial TEAE or TESAE report, the Investigator is required to proactively follow each Participant at subsequent Visits/contacts. All TEAEs, TESAEs, and AESIs (see Section 8.3.4) will be followed until resolution, stabilization, the event is otherwise explained, or the Participant is lost to follow-up (as defined in Section 10.2.3, Appendix 2).

8.3.6. Regulatory Reporting Requirements for TESAEs

Prompt notification by the Investigator to Helixmith of an SAE is essential to ensure that legal obligations and ethical responsibilities towards the safety of Participants and the safety of a study drug under clinical investigation are met.

Helixmith has a legal responsibility to notify both the local regulatory authority and other regulatory agencies about the safety of a study drug under clinical investigation. The Sponsor will comply with country-specific regulatory requirements relating to safety reporting to the regulatory authority, Institutional Review Boards (IRBs), and Investigators.

For all studies, Investigator Safety Reports must be prepared for suspected unexpected serious adverse reactions (SUSARs) according to local regulatory requirements and Helixmith's policy and forwarded to Investigators as necessary.

An Investigator who receives an Investigator Safety Report describing a TESAE or other specific safety information (e.g., summary or listing of TESAEs) from the Sponsor will review and then notify the IRB if appropriate according to local requirements.

8.3.7. Helixmith's Responsibility

All TEAEs and TESAEs will be reported on an annual basis to FDA in accordance with the IND regulation (21 Code of Federal Regulations [CFR] 312). Per the 2010 FDA Guidance Document for Industry and Investigators "Safety Reporting Requirements for INDs and bioavailability (BA)/bioequivalence (BE) Studies," events categorized as "possibly" or "probably" related will

be treated as “suspected adverse reactions.” Events categorized as “definitely” related will be treated as an “adverse reaction” (adverse drug reaction, ADR).

All serious and unexpected study-drug-related adverse reactions (SUSARs) or suspected adverse drug reactions (SADRs) will be reported to FDA and to all participating Investigators in an IND Safety Report within 15 calendar days of the event after Helixmith determines that the suspected adverse reaction qualifies for reporting (21 CFR 312.32). Any unexpected fatal or life-threatening study-drug-related adverse reaction or suspected adverse reaction will be reported to the Agency within 7 calendar days after the Sponsor’s initial receipt of the information.

Helixmith will notify all participating Investigators of any new safety information that alters the current risk-benefit assessment of the study medication or that would be sufficient to consider changes in Engensis administration or in the overall conduct of the study.

8.3.8. Pregnancy and Contraception

8.3.8.1. Pregnancy Test (Women of Childbearing Potential Only) and Contraception

Female Participants must be nonpregnant, nonlactating, and either postmenopausal for at least 1 year, or surgically sterile for at least 3 months, or agree to use double-barrier contraception from 14 days prior to Day 180 visit in VMALS-002-2 and/or their last confirmed menstrual period prior to Day 180 (whichever is longer) until 2 months after the last visit on Day 365/ET. Double-barrier contraception may include, but is not limited to, intrauterine device with spermicide, female condom with spermicide, diaphragm with spermicide, cervical cap with spermicide; having a male sexual partner who agrees to use a male condom with spermicide; or having a sterile sexual partner.

For women of childbearing potential, a urine beta human chorionic gonadotropin (β -HCG) test will be performed on Day 365/ET to evaluate whether the Participant is pregnant.

The rhythm method, abstinence, outercourse, or celibacy are not considered acceptable method of contraception.

8.3.8.2. Pregnancy

The Investigator will collect pregnancy information on any female Participant who becomes pregnant while participating in this study. The initial information will be submitted to the Helixmith within 24 hours of learning of a Participant’s pregnancy.

Further dosing will be discontinued for any female Participant who becomes pregnant during the study.

The Participant will be followed to determine the outcome of the pregnancy. The Investigator will collect follow-up information on the Participant and the neonate, and the information will be forwarded to Helixmith. Generally, follow-up will not be required for longer than 6 to 8 weeks beyond the estimated delivery date.

While pregnancy itself is not considered to be a TEAE or TESAE, any pregnancy complication or elective termination of a pregnancy for medical reasons will be reported as a TEAE or TESAE. A spontaneous abortion (occurring at < 22 weeks gestational age) or stillbirth (occurring at > 22 weeks gestational age) is always considered to be a TESAE and will be reported as such. Other abnormal pregnancy outcomes (e.g., fetal death, congenital anomalies, ectopic pregnancy) are also considered TESAEs and will be reported.

Any post-study pregnancy-related SAE considered possibly, probably, or definitely related to the study drug by the Investigator will be reported to the Helixmith. While the Investigator is not obligated to actively seek this information in former study Participants, he or she may learn of an SAE through voluntary reporting.

The Investigator will record a narrative description of the course of each pregnancy and its outcome.

8.3.9. Disease-Related Events and/or Disease-Related Outcomes Not Qualifying as AEs or SAEs

Except for signs and symptoms of ALS, all disease-related events or disease-related outcomes qualify as TEAEs or TESAEs.

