8.3. Treatment-emergent Adverse Events and Treatment-emergent Serious Adverse Events

The definitions of TEAEs and TESAEs can be found in Section [10.2](#), Appendix 2.

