9.3.1. Primary Endpoints

Safety analyses in this study will evaluate the safety profile of Engensis. The primary endpoints for safety are as follows:

- Incidence of TEAEs, TESAEs, and AESIs
- Incidence of clinically significant laboratory values

No formal statistical testing will be conducted for the safety analyses. All Participants in the Safety Population will be included in these analyses. For data analysis, Participants will be grouped by the treatment received during VMALS-002-2. All summaries will be derived from and based on available data. No imputation will be performed for missing values. All safety analyses will be made on the Safety Population.

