- The disease/disorder being studied or expected progression, signs, or symptoms of the disease/disorder being studied, unless more severe than expected for the Participant's

condition.

- Medical or surgical procedure (e.g., endoscopy, appendectomy): the condition that leads to the procedure is the TEAE.
- Situations in which an untoward medical occurrence did not occur (social and/or convenience admission to a hospital).
- Anticipated day-to-day fluctuations of pre-existing disease(s) or condition(s) present or detected at the start of the study that do not worsen.

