10.2.2. Criteria for Defining a TESAE

If an event is not a TEAE per the definition above, then it cannot be an TESAE even if serious conditions are met (e.g., hospitalization for signs/symptoms of the disease under study, death due to progression of disease).

An TESAE is defined as any untoward medical occurrence that at any dose:

a. Results in death

b. Is life-threatening

The term “life-threatening” in the definition of “serious” refers to an event in which the Participant was at risk of death at the time of the event. It does not refer to an event, which hypothetically might have caused death, if it were more severe.

c. Requires inpatient hospitalization or prolongation of existing hospitalization

- In general, hospitalization signifies that the Participant has been detained (usually involving at least an overnight stay) at the hospital or emergency ward for observation and/or treatment that would not have been appropriate in the physician’s office or outpatient setting. Complications that occur during hospitalization are AEs. If a complication prolongs hospitalization or fulfills any other serious criteria, the event is serious. When in doubt as to whether “hospitalization” occurred or was necessary, the TEAE should be considered serious.
- Hospitalization for elective treatment of a pre-existing condition that did not worsen from Baseline is not considered an SAE.

d. Results in persistent disability/incapacity

- The term “disability” means a substantial disruption of a person’s ability to conduct normal life functions.
- This definition is not intended to include experiences of relatively minor medical significance such as uncomplicated headache, nausea, vomiting, diarrhea, influenza, and accidental trauma (e.g., sprained ankle), which may interfere with or prevent everyday life functions but do not constitute a substantial disruption.

e. Is a congenital anomaly/birth defect

f. Other situations:

- Medical or scientific judgment should be exercised in deciding whether SAE reporting is appropriate in other situations such as important medical events that may not be immediately life-threatening or result in death or hospitalization but may jeopardize the Participant or may require medical or surgical intervention to prevent one of the other outcomes listed in the above definition. These events should usually be considered serious.

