it is an intentional overdose taken with possible suicidal/self-harming intent. Such overdoses should be reported regardless of sequelae.

Events NOT Meeting the TEAE Definition

- Any clinically significant abnormal laboratory findings or other abnormal safety assessments that are associated with the underlying disease, unless judged by the Investigator to be more severe than expected for the Participant's condition.
- The disease/disorder being studied or expected progression, signs, or symptoms of the disease/disorder being studied, unless more severe than expected for the Participant's condition.
- Medical or surgical procedure (e.g., endoscopy, appendectomy): the condition that leads to the procedure is the TEAE.
- Situations in which an untoward medical occurrence did not occur (social and/or convenience admission to a hospital).
- Anticipated day-to-day fluctuations of pre-existing disease(s) or condition(s) present or detected at the start of the study that do not worsen.

6.14.1.2 Treatment Emergent Serious Adverse Event (TESAE) Definition:

Any untoward medical occurrence that, at any dose:

- Results in death
- Is life-threatening

The term “life-threatening” in the definition of “serious” refers to an event in which the Participant was at risk of death at the time of the event. It does not refer to an event, which hypothetically might have caused death, if it were more severe.

- Requires inpatient hospitalization or prolongation of existing hospitalization
 - In general, hospitalization signifies that the Participant has been detained (usually involving at least an overnight stay) at the hospital or emergency ward for observation and/or treatment that would not have been appropriate in the physician's office or outpatient setting. Complications that occur during hospitalization are AEs. If a complication prolongs hospitalization or fulfills any other serious criteria, the event is serious. When in doubt as to whether “hospitalization” occurred or was necessary, the TEAE should be considered serious.
 - Hospitalization for elective treatment of a pre-existing condition that did not worsen from Baseline is not considered an SAE.

QMD Ref: Worldwide-TMP-ST-005-7.0 Effective: 12Aug2019	Governing QMD: Worldwide-SOP-ST-001
Confidentiality Statement	

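### Protocol 8.3.9 drops all signs and symptoms of ALS from TEAEs and TESAEs, while Protocol 10.2.1 and SAP 6.14.1.1 keep those worse than expected; the rules on progression deaths also disagree

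*Protocol*

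**What the plan says.** Protocol 8.3.9, whose heading concerns disease-related events that do not qualify as AEs or SAEs, consists of one sentence: "Except for signs and symptoms of ALS, all disease-related events or disease-related outcomes qualify as TEAEs or TESAEs". It carries no severity qualifier and no cross-reference.

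Protocol 10.2.1 (Appendix 2) lists among the events that are not TEAEs the disease itself and "expected progression, signs, or symptoms of the disease/disorder being studied, unless more severe than expected" for that participant. SAP 6.14.1.1 repeats this: "expected progression, signs, or symptoms of the disease/disorder being studied, unless more severe than expected for the Participant's condition".

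For serious events, Protocol 10.2.2 says "If an event is not a TEAE per the definition above, then it cannot be an TESAE even if serious conditions are met", and gives as examples "hospitalization for signs/symptoms of the disease under study, death due to progression of disease". SAP 6.14.1.2 gives the seriousness criteria, including death, but leaves out that opening rule and its examples.

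Protocol 8.3 sends the reader to Appendix 2: "The definitions of TEAEs and TESAEs can be found in Section" 10.2. No text says which section prevails. Protocol 9.3.1 makes "Incidence of TEAEs, TESAEs, and AESIs" a primary endpoint, summarized descriptively from available data without imputation.

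**The concern.** The same event can be classified in two ways. An ALS sign that is worse than expected is a TEAE under Appendix 2 and the SAP, and is not one under 8.3.9. By 10.2.2, an event kept out of the TEAEs is also kept out of the TESAEs.

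This matters because Engensis is meant to act on motor neurons, so unexpectedly fast ALS worsening is a harm that a long-term safety study should be able to show. In the TEAE definition, the worse-than-expected clause is what lets such worsening in. Investigator causality assessment (10.2.4) and 24-hour reporting of serious events (8.3.1) are tied to the TEAE or TESAE label. The SAP definition is applied after collection and cannot restore an event that no site recorded.

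**Working it through.** The documents give no figure to reproduce: sample size is set by rollover, and the safety analysis involves no testing. The check is mainly a comparison of texts.

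**Classification under each text**

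| Event | Protocol 8.3.9 | Protocol 10.2.1 and 10.2.2 | SAP 6.14.1.1 and 6.14.1.2 |
|---|---|---|---|
| ALS sign or symptom, as expected | Not a TEAE | Not a TEAE | Not a TEAE |
| ALS sign or symptom, worse than expected | Not a TEAE | TEAE | TEAE |
| Death due to ALS progression | TEAE or TESAE, read as a disease-related outcome | Cannot be a TESAE | Death is a criterion; the progression exclusion is absent |

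The texts agree only on the first row. In the second row, 8.3.9 stands alone against the other two. In the third, 8.3.9 and 10.2.2 give opposite answers, and the SAP does not carry the 10.2.2 exclusion.

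**What the AESI list still catches.** Protocol 8.3.4.2 covers pulmonary events, new or worsening bulbar disease, and progressive weakness, described in these terms: "some patients with ALS may develop rapidly progressive muscle weakness that results in loss of ability to care for self", with decubitus ulcers and weight loss from impaired swallowing as further consequences. Protocol 8.3.4 requires these to be recorded as AESIs and the serious ones to be reported as TESAEs. AESIs are part of the primary endpoint and have their own table (SAP Table 14.3.1.9). Outside the list are, for example, spasticity and cognitive impairment, both part of the ALS presentation in Protocol 2.2.1, and weakness without the listed consequences. These are the events most exposed to 8.3.9.

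**Weight of one participant.** The maximum N is 18 (Protocol synopsis; SAP 4). If a participant's only counted event is unrecorded, incidence moves by 1/n:

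- Overall: 1/18 = 5.6 percentage points.
- By arm (the split is not given, so sizes are assumed): 1/12 = 8.3, 1/9 = 11.1, 1/6 = 16.7 points.

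The condition matters. In VMALS-001, 17 of 18 participants (94.4%) had at least one AE, with 79 events in all (Protocol synopsis). At a similar rate, the share with any TEAE over both studies would barely change. A 1/n shift is more plausible for a single preferred term, or for the set of TEAEs starting in the extension (SAP 6.14.1).

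**Progression deaths, as an illustration only.** In VMALS-001, 1 of 18 died before the 9-month visit and 14 of the remaining 17 died later, up to month 36, all from respiratory failure associated with ALS (Protocol 2.2.6.1). Assuming a constant hazard after month 9:

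- Hazard = -ln(3/17)/27 = 0.0642 per month.
- Risk over months 9 to 12 = 1 - exp(-3 x 0.0642) = 17.5%, and 17 x 0.175 = 3.0 deaths.
- With the one earlier death, about 4 of 18 (22%). If that death came before Day 180, such a participant could not have entered an extension, and about 3 of 17 applies.

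**The case against.** Four points weigh against the concern.

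- **Sites are directed to Appendix 2.** Protocol 8.3, 8.3.1 and 8.3.2 all refer to Section 10.2, so a careful site may apply the qualified wording. This stands, and it makes the loss possible rather than certain. It does not remove the conflict: 8.3.9 is a specific rule within 8.3, with no precedence statement.
- **Much rapid worsening is recorded anyway.** The AESI route above stands. Protocol 8.1.5 and 8.1.1 also send clinically significant SVC and examination findings to TEAEs, TESAEs or AESIs. The AESI table does not, however, repair the TEAE and TESAE tables, and the AESI list is itself largely made up of ALS signs, so it too is at odds with 8.3.9.
- **Decline and death are measured directly.** ALSFRS-R, HHD and SVC are scheduled at every visit and summarized by arm. Tracheostomy and all-cause mortality have Kaplan-Meier analyses, and the DSMB reviews pooled mortality. A reader might infer that faster decline after Engensis would go unseen; the documents do not support that. These endpoints are exploratory, though, and carry no causality assessment.
- **No direction of bias is shown.** A reader might also infer that the omission favors Engensis. Follow-up is blinded (Protocol 6.1.1 and 6.1.2) and the wording applies to both groups, so the documents give no basis for that.

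A reader might further infer that TESAE incidence from progression deaths would read 0% under one section and up to 22% under another. That is too strong. The upper figure rests on an assumed hazard and counts from injection, although entry requires completing Day 180. The 0% ignores that respiratory arrest is an AESI, to be reported as a TESAE when serious.

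**Conclusion.** The inconsistency is real. Protocol 8.3.9 differs from Protocol 10.2.1 and SAP 6.14.1.1 on unexpectedly severe ALS worsening. It also differs from 10.2.2 on death due to progression, where SAP 6.14.1.2 departs from 10.2.2 as well. A site that follows 8.3.9 literally could leave such worsening out of the TEAE and TESAE components of the primary endpoint, and the analysis could not recover it.

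The consequence is bounded. It falls mainly on ALS signs outside the AESI list and on the TEAE and TESAE tables. Its size is 5.6 points overall for each participant whose only counted event is missed, or 8 to 17 points within an arm, assuming arms of 12 to 6. Any range for progression deaths is illustrative. The point deserves correction because the endpoint is primary, the sample is small and the repair is cheap.

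**What to change.** Reconcile Protocol 8.3.4 to 8.3.4.2, 8.3.9, 10.2.1 and 10.2.2 with SAP 6.14.1.1 and 6.14.1.2, so that one rule governs both recording and analysis:

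- Align 8.3.9 with the qualified exclusion already in Protocol 10.2.1 and SAP 6.14.1.1, so that ALS signs and symptoms worse than expected for the participant are recorded.
- State one classification for deaths and hospitalizations due to progression, and write it into Protocol 8.3.9 and 10.2.2 and into SAP 6.14.1.2. Matching the current texts is not enough, because 10.2.2 and SAP 6.14.1.2 differ from each other.
- Say how that rule applies to the ALS-related AESIs in 8.3.4.2.
- Ask sites to recheck events withheld under 8.3.9.

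The cost is a one-paragraph protocol clarification, a matching SAP line and a site letter. The downside is possibly a few more recorded TEAEs.
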